#### Randomization

Randomization will be conducted in blocks of five to a ratio of 4:1 (active:placebo). Qualified subjects will be enrolled and randomized in: 8:8:8:8:8:10 ratio to either Nu-3 at one of five possible dose levels (0.1%, 1%, 2%, 5% and 10% Nu-3 solution in saline (w/v)), or to placebo, respectively.

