### **Diabetic Foot Ulcer Wound Infection Score**

Parameter	Wound Infection Score			
	0	1	2	3
Purulent discharge	Absent			Present
Nonpurulant drainage (serious, sanguinous)	Absent	Mild		
Erythema	None	Mild pink, barely perceptible	Moderate pale red, defined edges	Severe red to dark red
Induration	None	Mild	Moderate	Severe
Tenderness (sign)	None	Mild	Moderate	Severe
Pain (symptoms)	None	Mild	Moderate	Severe
Local Warmth (relative to uninfected contralateral foot)	Same	Mildly increased	Moderately increased	Severely increased

Photo Documentation and Calculation of the Ulcer Area and Depth using the Aranz Medical SilhouetteTM as described in Appendix A

A past medical/surgical history will be recorded for any conditions or treatments that are, in the opinion of the investigator, relevant to the current diagnosis. The previous condition will be recorded as a diagnosis rather than a previous symptom. The time of the previous diagnosis relative to the current admission will be provided (i.e., "6 months ago") to the best of the patient's knowledge. If the diagnosis was more than two years ago, then it can be recorded as "more than two years ago".

Prior medications will be recorded. Prior medications include medications that the patient is currently taken or has taken within the past fourteen days.

Physical examinations are performed at screening by the investigator or designee. The screening examinations will include general appearance, height, weight, skin, neck, eyes, ears, nose, throat, heart, lungs, abdomen, cervical and axillary lymph nodes, extremities, and nervous system. Height is measured in stocking or bare feet, and recorded in centimeters (cm). Weight is recorded in kilograms (kg).

Results of these investigations/assessments and baseline measurements obtained from the local laboratory will be reviewed by the Investigator prior to the start of the treatment. Patients who do not meet study entry criteria will be promptly notified and excluded from further participation in the study. Patients who continue to meet entry criteria will be enrolled in the study and assigned a patient number by the database. The patient can be randomized at any time following the screening.

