## 3. STUDY OVERVIEW

This is a phase 1/2a prospective, multi-center, blinded, randomized, dose escalation study. This study will be conducted at four investigational sites. Subjects with diabetic chronic foot ulcer(s) and a Diabetic Ulcer Severity Score (DUSS) of 0 to 3, ulcerated area(s) of not more than two ulcers between 0.5 and 6 cm^2, and no underlying DUSS Probing to Bone='Yes' are eligible to be enrolled into the study.

Doses of Nu-3 will be escalated in three planned sequential cohorts with 10 subjects in each cohort. Randomization will be 4:1 active to placebo in each cohort. The dose levels in each cohort are:

- Cohort 1 – 0.1% solution of Nu-3 in 0.9% saline with vehicle
- Cohort 2 – 1% solution of Nu-3 in 0.9% saline with vehicle
- Cohort 3 – 2% solution of Nu-3 in 0.9% saline with vehicle

Each cohort has placebo defined as 0.9% saline with vehicle. Dosing will be twice daily for 7 consecutive days.

Subjects will have scheduled study visits as follows:

- Screening (Day -7 to -4 hours)
- Single dose visit (Day 1)

- Safety review and multiple dose visit (Day 2)
- Safety review visit (Day 9  $\pm$ 1 day)
- Final Visit (Day 15  $\pm$ 2 days)

At the conclusion of each cohort, a Safety Review Committee will review the safety data and determined if it is safe to proceed to the next cohort. The committee includes, but is not limited to the Sponsor's designated Medical Monitor, the Medical Director of the CRO, and the Medical Director of Lakewood Amedex. Additional members can be added as the sponsor deemed appropriate.

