#### **4. GENERAL ANALYSIS CONSIDERATIONS**

The statistical analyses will be reported using summary tables and data listings. For all efficacy parameters, a comparison will be made of each active treatment group versus placebo using the appropriate statistical test. Unless otherwise indicated, all statistical tests will be two-sided and differences will be considered statistically significant if the associated p-value is less than 0.05. Continuous variables will be summarized with means, standard deviations (SD), medians, minimums, and maximums. Categorical variables will be summarized by counts and by percentage of subjects in corresponding categories. All data will be summarized by dose group (cohort), with all placebo subjects combined into one placebo arm.

Individual subject data obtained from the electronic data capture system, study lab, and any derived data will be presented by cohort for each subject in data listings.

The analyses described in this plan are considered *a priori*, in that they have been defined prior to database lock for individual subjects. Any analyses performed subsequent to database lock will be considered post-hoc and exploratory. Post-hoc analyses will be identified in the CSR.

All analyses and tabulations will be performed using SAS® Version 9.4 or higher on a Windows platform. Tables and listings will be presented in PDF format. Upon completion, all SAS® programs will be validated by an independent programmer. In addition, all program output will undergo a senior level statistical review. The validation process will be used to confirm that statistically valid methods have been implemented and that all data manipulations and calculations are accurate. Checks will be made to ensure accuracy, consistency with this plan, consistency within tables, and consistency between tables and corresponding data listings. Upon completion of validation and quality review procedures, all documentation will be collected and filed by the project statistician or designee.

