## **8. EFFICACY ANALYSIS**

### **8.1 Definition of Efficacy Endpoints**

All efficacy endpoints will be summarized by visit and evaluated statistically at the end of the MAD portion of the study. Efficacy endpoints include:

- The proportion of subjects with a normal culture
- The change from baseline in the DUSS score
- The change from baseline in the DFI score
- The absence of each of the following as reported by the investigator on the CRF:
  - Purulent discharge
  - Nonpurulent drainage
  - Erythema
  - Induration
  - Tenderness
  - PainLocal warmth (no change)
- Data captured on the total wound size for each subject using the Aranz Medical Silhouette™ System:
  - Wound area (cm^2)

- Percentage of area reduction
- Perimeter (mm)
- Maximum depth (mm)
- Mean depth (mm)
- Volume (cm^3)
- Length (mm)
- Width (mm)

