## **8.2 Analysis of Efficacy Endpoints**

For each dose group, the proportion of subjects with a normal culture at the end of the MAD portion of the study will be compared to the proportion of subjects with a normal culture at the end of the MAD portion of the study for the combined placebo group using a Fisher's exact test. A subject with a normal culture at this time will be considered a success. Any subject with a missing value at the end of the MAD portion of the study will not be included in the analysis. A p-value less than 0.05 will be considered statistically significant and a p-value less than 0.0167, employing a Bonferroni correction for multiple comparisons, will be considered highly conclusive.

For continuous efficacy endpoints, data will be summarized descriptively at and a comparison using the Wilcoxon Rank Sum test between each of dose groups and the combined placebo group will be performed at each visit. For these endpoints, no imputation for missing values will be performed.

For categorical endpoints, a Fisher's exact test will be performed in a similar manner. Subjects missing a value for a secondary endpoint will be considered a failure (counted in the denominator) for that endpoint.

For all tests, a p-value less than 0.05 will be considered statistically significant and a p-value less than 0.0167, employing a Bonferroni correction for multiple comparisons, will be considered highly conclusive. Analysis for each secondary endpoint will be performed on the ITT population and the PP population.

Ulcer measurements and percentage of area reduction will be summarized descriptively by visit and statistical testing using a Wilcoxon Rank Sum test between each dose group and the combined placebo group. For all tests, a p-value less than 0.05 will be considered statistically significant. Analysis for each additional endpoint will be performed on the ITT population and the PP population.

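### Change in DFI score is tested without baseline adjustment although baseline DFI is collected: a loss of power rather than of validity, whose size rests on assumptions

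*SAP*

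**What the plan says.** SAP 8.1 lists "The change from baseline in the DFI score" among the efficacy endpoints. It says that endpoints are summarised by visit and tested at the end of the multiple-dose (MAD) period. For continuous endpoints SAP 8.2 states that a "comparison using the Wilcoxon Rank Sum test between each of dose groups and the combined placebo group will be performed at each visit". It does not impute missing values and names no covariate, no baseline-adjusted model and no sensitivity analysis. I read the DFI change as one of these continuous endpoints, since the section's other rules concern culture, categorical endpoints and ulcer measurements.

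SAP 4 sets the level: "all statistical tests will be two-sided and differences will be considered statistically significant if the associated p-value is less than 0.05". SAP 8.2 adds that "a p-value less than 0.0167, employing a Bonferroni correction for multiple comparisons, will be considered highly conclusive".

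Group sizes follow from SAP 3, which describes "three planned sequential cohorts with 10 subjects in each cohort. Randomization will be 4:1 active to placebo in each cohort", and from SAP 4, which summarises data "with all placebo subjects combined into one placebo arm". The protocol synopsis, under Randomization, has five dose levels and an "8:8:8:8:8:10 ratio", the last figure being placebo.

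The score is defined in the protocol table headed "Diabetic Foot Ulcer Wound Infection Score", which grades seven signs and symptoms of infection. The Schedule of Events (Protocol section 2) has it rated at Visit 1, Visit 4 (Day 9) and Visit 5 (Day 15). Protocol 9.1 sets no DFI range for entry. SAP 10 says that no sample size calculation was done.

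**The concern.** DFI is the only composite score of infection signs in the trial. DUSS grades pulses, probing to bone, ulcer location and ulcer number, none of which is a sign of infection. Assessing clinical response is a secondary objective, and the DFI tests carry the labels for significance and for being highly conclusive, so it matters that the analysis uses the data well.

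A raw change depends on where the subject started. Someone who enters at 2 can improve by at most 2 points; someone who enters at 12 can improve by 12. Regression to the mean works in the same direction. With no DFI limit on entry and very small groups, a good deal of the spread in the change score can be entry severity rather than treatment. A model with baseline DFI as a covariate removes that part. The plan leaves it in, although the covariate is collected.

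**Working it through.** **Inputs from the documents**
- Per comparison in the SAP: 8 active per dose; placebo 3 cohorts x 2 = 6, so 8 v 6.
- Per comparison in the protocol: 8 v 10.
- Two-sided level 0.05. The second threshold reproduces as 0.05/3 = 0.0167.
- DFI maximum: purulent discharge 3 + nonpurulent drainage 1 + five items x 3 = 19.
- There is no planned power figure to reproduce.

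**Assumptions** (the documents give none of these): true effect 0.5 to 2 SD of the follow-up score; correlation rho 0.3 to 0.9 between baseline and follow-up; equal SDs at both times; no dropout.

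**Step 1: variance.** In units of the score variance, the change score has 2(1 - rho) and linear ANCOVA has 1 - rho². At rho 0.5 these are 1.00 and 0.75, a ratio of (1 + rho)/2 = 0.75.

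**Step 2: normal approximation, 8 v 6, rho 0.5.** The standard error is SD x sqrt(1/8 + 1/6) = 0.540 x SD. At a 1 SD effect:
- change score: 1/0.540 - 1.96 = -0.11, power about 46%;
- ANCOVA: 1/(0.540 x 0.866) - 1.96 = 0.18, power about 57%.

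The largest gain by this formula is 63.9% to 76.2%, at 1.25 SD.

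**Step 3: simulation, unbounded normal scores, rho 0.5, 20,000 trials per cell.** Exact Wilcoxon on change against ANCOVA (t test, N - 3 df):

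| True effect | 8 v 6 | 8 v 10 |
|---|---|---|
| 0.5 SD | 11.5% to 15.5% | 15.2% to 20.4% |
| 0.8 SD | 24.2% to 32.0% | 31.5% to 42.3% |
| 1.0 SD | 35.3% to 46.4% | 45.3% to 59.5% |
| 1.5 SD | 66.3% to 79.7% | 79.7% to 91.0% |
| 2.0 SD | 89.0% to 95.8% | 96.4% to 99.1% |

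At rho 0.7 the gain is at most about 8 to 9 points. At rho 0.3 it reaches about 19 to 20.

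**Step 4: scores rounded and held to 0-19, assumed mean 6 and SD 3, 1 SD effect.** Wilcoxon on change against rank ANCOVA:

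| rho | 8 v 6 | 8 v 10 |
|---|---|---|
| 0.3 | 24% to 39% | 33% to 49% |
| 0.5 | 32% to 42% | 42% to 57% |
| 0.7 | 49% to 57% | 60% to 68% |

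On this bounded score, over both group sizes and both forms of adjustment, the gain at rho 0.5 is about 3 to 6 points at 0.5 SD, 10 to 16 at 1 SD and 15 to 20 at 1.5 SD. At rho 0.7 it is about 3 to 12.

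**Step 5: dependence on the floor.** With an assumed mean of 5 and SD of 2.5, the rho 0.5 gain from linear ANCOVA is 5, 16 and 25 points at 0.5, 1 and 1.5 SD. The unbounded scores in Step 3 give 11 to 13 at 1.5 SD. At large effects the figure therefore depends heavily on how close subjects enter to zero.

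**Step 6: size of the tests.** With no treatment effect, the Wilcoxon test rejects in about 3 to 5% of trials and linear ANCOVA in about 4 to 6%. Some of the gap is therefore the discreteness of the Wilcoxon test. When permutation p-values are used for both the Wilcoxon and rank ANCOVA (8 v 6, 1 SD), power goes from 33% to 43% at rho 0.5 and from 50% to 54% at rho 0.7.

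**Step 7: rank ANCOVA at high correlation.** On unbounded scores at rho 0.8 (8 v 10, 0.8 SD) it falls below the Wilcoxon, 62.8% against 65.7%. On the bounded score it is about level or slightly ahead at rho 0.8, and it loses a few points at rho 0.9 (8 v 6, 0.5 SD: 33% against 37%).

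**The case against.** The best case for leaving the plan alone is that little turns on this. The primary objective is safety and tolerability, the trial is an unpowered pilot, and DFI change is one of many efficacy endpoints. A rank test on change is a conventional choice for a small ordinal score. At 8 v 6 and rho 0.5, neither method reaches 50% power at a 1 SD effect. All of that stands, and it sets the priority. It does not show that the baseline should be discarded, because using it needs no new data.

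Four stronger readings are tempting, and the documents do not support them.

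- **That imbalance in entry severity makes the planned test misleading.** By chance alone, a difference in mean baseline above 0.5 SD will occur in roughly a third of 8 v 6 comparisons (0.5/0.540 = 0.93 standard errors). That is random variation which the test already allows for. Pooling placebo over sequential cohorts does mean that only 2 of the 6 placebo subjects were randomised alongside a given dose. If a dose group came from a population 1 SD sicker at entry, the Wilcoxon on change would reject falsely about 8 to 14% of the time, against 5 to 6% for rank ANCOVA; at a 0.5 SD shift it is 5 to 6%. Those shifts are assumed. The entry criteria are the same for every cohort, and nothing in the documents points to a drift.
- **That the loss is one number, such as 12 points.** That figure needs rho near 0.5 and an effect near 1 SD, neither of which the documents give.
- **That the change score is noisier at every correlation below 1.** This is true of linear ANCOVA against a linear change score (Step 1). It is not true of rank ANCOVA against the Wilcoxon (Step 7).
- **That DFI change is the only way to see an infection response.** SAP 8.1 also lists the absence of each DFI sign and the proportion with a normal culture.

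**Conclusion.** The point holds as one of efficiency. SAP 8.2 compares raw DFI change without adjustment while a usable baseline is collected at Visit 1, and adjusting for it would usually raise power. Type I error is controlled under randomisation, provided that pooled placebo subjects are comparable across cohorts.

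The size is conditional. The ranges in Step 4 assume a 0-19 score with mean 6 and SD 3, equal SDs and no dropout. They widen at large effects if subjects enter nearer the floor, and they include a contribution from the conservative size of the Wilcoxon test. This is a free improvement of minor priority. It does not call the safety objective or the design into question.

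**What to change.** In SAP 8.2, for DFI only:

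1. Make the main analysis an ANCOVA of end-of-MAD DFI on baseline DFI and dose group, each dose against pooled placebo. Name the visit; I take it to be Visit 4 (Day 9). This also settles, for DFI, the difference between SAP 8.1 (test at the end of MAD) and SAP 8.2 (test at each visit).
2. Take the p-value from a permutation of the group labels, because the groups are small and the score is bounded. Full enumeration is feasible: 3,003 allocations for 8 v 6 and 43,758 for 8 v 10. Like the planned Wilcoxon, this treats placebo subjects as exchangeable across cohorts.
3. Report the baseline-adjusted mean difference with its 95% CI. For a pilot that informs dose range this is more useful than the p-value.
4. Keep the Wilcoxon test on change as a sensitivity analysis. The thresholds of 0.05 and 0.0167 need not change.

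The cost is one model degree of freedom, some SAP wording and a little SAS programming. No subjects are lost, since the change score already needs both measurements. If a rank ANCOVA is preferred, the SAP should say that it gains less than the linear model and can lose a few points of power against the Wilcoxon at very high correlation (about 0.8 to 0.9). The change should be made before database lock and unblinding.

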## **9. SAFETY ANALYSES**

For all safety analyses, the safety population will be used.

### **9.1 Adverse Events**

All AE summaries will be restricted to Treatment-Emergent Adverse Events (TEAE), which are

defined as those AEs that occurred after dosing and those pre-existing AEs that worsened during the study. Verbatim terms on case report forms will be mapped to preferred terms and system organ classes using the MedDRA dictionary (version 14.1).

Each AE summary will be displayed by dose group. Summaries that are displayed by system organ class and preferred terms will be ordered by descending order of incidence of system organ class and preferred term within each system organ class. Summaries of the following types will be presented:

- Subject incidence of TEAEs and total number of unique TEAEs by MedDRA system organ class and preferred term.
- Subject incidence of TEAEs by MedDRA system organ class, preferred term, and highest severity. At each level of subject summarization, a subject is classified according to the highest severity if the subject reported one or more events. An event with missing severity will not be imputed.
- Subject incidence of TEAEs by MedDRA system organ class, preferred term, and closest relationship to study drug (Not Related, Unlikely, Possibly, Probable, Definite). At each level of subject summarization, a subject is classified according to the closest relationship if the subject reported one or more events. AEs with a missing relationship will be considered definite related for this summary.
- Subject incidence of serious TEAEs and total number of unique serious TEAEs by MedDRA system organ class and preferred term.

## 9.2 Vital Signs

Vital sign assessments will be analyzed by dose group at baseline and each scheduled post-baseline visit. Mean observed measurements and mean changes from baseline will be summarized. Baseline is defined as the last non-missing value obtained prior to receiving study drug.

An outlier analysis will be performed to provide counts and percentage of subjects above or below certain cutoffs for specific vital sign parameters. The following cutoffs will be used in the outlier analysis for the vital signs data:

### Heart Rate

- Any post-baseline value > 120 bpm or > 130 bpm
- Any increase from baseline of  $\geq 20$  bpm or  $\geq 30$  bpm

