#### **Study Design**

Multi center, Randomized Double Blind, Placebo-Controlled, Dose Escalating Study

Clinical investigation Objective(s) and Endpoint:

	Objective	Endpoint	Variable
Primary	To assess the safety and tolerability of escalating doses of topically applied bisphosphocin™ Nu-3	Treatment emergent events related to clinical investigation product	
 
Vital signs,
 
CBC analysis, CMP analysis,
 
Physical examination,
 

Secondary	• To assess the clinical and microbiological response to bisphosphocin™ Nu-3	

Reduction of pathogenic bacteria

Visual evaluation of the ulcer

	

Aerobic and anaerobic culture and sensitivity

DUSS Score

	• To support determination of the appropriate dose range of Nu-3 to be employed in future clinical studies.		

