### Systolic Blood Pressure

- Any post-baseline value > 150 mmHg or < 90 mmHg
- Any increase from baseline of  $\geq 20$  mmHg or  $\geq 30$  mmHg
- Any decrease from baseline of  $\geq 20$  mmHg or  $\geq 30$  mmHg

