### Diastolic Blood Pressure

- Any post-baseline value > 100 mmHg or < 50 mmHg
- Any increase from baseline of  $\geq 20$  mmHg or  $\geq 30$  mmHg
- Any decrease from baseline of  $\geq 20$  mmHg or  $\geq 30$  mmHg

The above outlier analysis will be conducted for post-baseline vital sign assessments collected throughout the entire study period.

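### The heart-rate outlier analysis in SAP 9.2 looks only upward, so it cannot count a fall in heart rate

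*SAP*

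**What the plan says.** SAP 9.2 (Vital Signs) states the purpose of the outlier analysis: to "provide counts and percentage of subjects above or below certain cutoffs for specific vital sign parameters". It then lists criteria for three parameters.

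- **Heart rate:** "Any post-baseline value > 120 bpm or > 130 bpm", and one change bullet, which begins "Any increase from baseline of" and uses steps of 20 and 30 bpm.
- **Systolic pressure:** "Any post-baseline value > 150 mmHg or < 90 mmHg", an increase bullet, and a bullet that begins "Any decrease from baseline of", both with steps of 20 and 30 mmHg.
- **Diastolic pressure:** "Any post-baseline value > 100 mmHg or < 50 mmHg", with increase and decrease bullets at the same steps.

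The results go into Table 14.3.2.2 and, for heart rate, Listing 16.2.13.2. The SAP gives no reason for treating heart rate differently from blood pressure. In the objectives table of the protocol synopsis, vital signs are one of the variables under the primary safety objective, whose endpoint is "Treatment emergent events related to clinical investigation product".

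**The concern.** Both pressures are screened in both directions and heart rate in one, under an introduction that speaks of both. A subject whose heart rate went from 72 to 38 bpm would meet no heart-rate criterion; a subject who went from 72 to 125 bpm would meet both the value and the change criterion.

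Listing 16.2.13.2 is titled as subjects with outlying heart rate, with no direction given. A reader of the study report who finds no low values there could take that as a result, when the rule cannot produce any. This matters somewhat more than usual because Protocol 8.8 describes a first-in-human study and Protocol 15 plans no pharmacokinetic assessment, so routine safety measurements carry much of the information.

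The value bullet is also unclear. The matching bullets for both pressures pair an upper with a lower limit, while here both limits are upper. A programmer cannot tell from the text whether to build two rows (above 120, above 130) or whether the second limit is a slip for a lower one.

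**Working it through.** The plan gives no figure to reproduce: SAP 10 states that no sample size was calculated, and the outlier analysis carries no test. The check is of the rule's logic, followed by the cost of the proposed addition.

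**1. Criteria side by side (SAP 9.2)**

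| Criterion | Heart rate | Systolic | Diastolic |
|---|---|---|---|
| Upper limit | > 120, > 130 bpm | > 150 mmHg | > 100 mmHg |
| Lower limit | none | < 90 mmHg | < 50 mmHg |
| Increase | ≥ 20, ≥ 30 bpm | ≥ 20, ≥ 30 mmHg | ≥ 20, ≥ 30 mmHg |
| Decrease | none | ≥ 20, ≥ 30 mmHg | ≥ 20, ≥ 30 mmHg |

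**2. What the rules flag.** The criteria were applied as written to every pair of whole-number baseline and later values in which the later value is lower. The ranges are illustrative.

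- Heart rate, baseline 50 to 120 bpm, later value from 20 bpm up: 4615 falls, 0 flagged. Of these, 3266 are falls of at least 20 bpm.
- Heart rate, baseline 121 to 180 bpm: 7830 falls, 1770 flagged, all because the later value is still above 120 and none because it fell.
- Systolic, baseline 100 to 150 mmHg, falls of at least 20 mmHg: 2346 of 2346 flagged.
- Diastolic, baseline 55 to 100 mmHg, falls of at least 20 mmHg: 1311 of 1311 flagged.
- Heart rate with a mirrored decrease criterion of at least 20 bpm: 3266 of 3266 flagged.

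**3. The 120/130 bullet.** As a single condition, every value above 130 is already above 120, so the second limit adds no subject. As two tiers it adds a second, nested row. Neither reading counts anything low.

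**4. What other outputs would show.** One subject in a dose group of 8 falling by 40 bpm moves the group mean change by 40 / 8 = 5 bpm. SAP 4 also gives minimums and maximums for continuous variables, so the same subject would normally be visible as the group's minimum. A minimum shows one extreme value, not how many subjects had a large fall.

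**5. Noise cost of a decrease criterion.** The number of readings comes from the protocol. SAP 9.2 defines baseline as the last value before study drug, and Protocol 12.3 takes Day 1 vital signs within 10 minutes before treatment. The scheduled post-baseline visits are therefore Days 2, 9 and 15, so k = 3.

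Assume no drug effect and independent normal readings about a subject's own mean, with SD s of 6, 8 or 10 bpm. No document gives s. With Φ and φ the standard normal distribution function and density, the chance of at least one fall of c bpm or more is

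P = ∫ φ(z) {1 − [1 − Φ(z − c/s)]^k} dz.

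| | s = 6 | s = 8 | s = 10 |
|---|---|---|---|
| c = 20, k = 3 | 2.4% | 9.3% | 17.7% |
| c = 30, k = 3 | 0.06% | 1.1% | 4.4% |
| c = 20, k = 4 | 3.1% | 11.5% | 21.2% |
| c = 30, k = 4 | 0.08% | 1.4% | 5.5% |

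The k = 4 rows apply if a post-dose Day 1 reading, which Protocol 12.9 permits, is also recorded. By symmetry the same rates hold for the increases already in the SAP. In the SAP's 30 subjects, the 20 bpm step with k = 3 means about 30 × 0.024 = 0.7 to 30 × 0.177 = 5.3 chance flags.

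**The case against.** The strongest reply is that a fall in heart rate is not lost to the trial. Minimums are planned under SAP 4, all values are in Listing 16.2.13.1, and Protocol 12.9 has deviations from normal blood pressure and heart rate after the Day 1 and Day 2 doses recorded as adverse events, which feed the adverse-event tables. This stands. A reader might infer that a fall could never surface in a primary safety variable; the documents do not support that, and the point is limited to the outlier analysis. The other routes are still not substitutes. The listing carries no flags. The Protocol 12.9 monitoring is optional, leaves normal undefined, and does not extend to the Day 9 visit after the 7-day course. None of them counts subjects.

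A second reply is that 120/130 are simply two reporting tiers. The SAP writes its 20/30 change steps the same way in five bullets, so calling the pair redundant holds only if it is one condition. This also stands; what remains is that the text does not settle the reading.

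Third, a reader might infer that Table 14.3.2.2 would report zero low-heart-rate outliers. It would not: no such row is specified, and an absent row is not a reported zero.

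Fourth, the protocol promises only a mean-change table for vital signs, so the outlier analysis is an SAP addition, and its introductory sentence need not promise both directions for every parameter. That is fair and keeps the point minor. It does not explain why heart rate alone is screened one way.

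**Conclusion.** The point holds in this limited form: the heart-rate outlier analysis is one-sided, against its own stated purpose and both blood-pressure rules, and cannot count a fall as a fall in Table 14.3.2.2 or Listing 16.2.13.2. This follows from the text and rests on no assumption about variability; the SDs affect only the estimated noise cost of the fix. It is a minor correction to one descriptive table and one listing. No efficacy result, significance level or dose-escalation rule changes. Whether 120/130 is a pair of tiers or a slip cannot be decided from the documents, and no absolute lower limit can be derived from them.

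**What to change.** In SAP 9.2, Heart Rate:

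1. Add a criterion for any decrease from baseline of at least 20 bpm or at least 30 bpm, mirroring the increase steps already there.
2. Reconcile the value bullet with the introduction to 9.2 and with the two blood-pressure rules: state whether 120 and 130 bpm are separate tiers, each with its own row, or a mistyped upper/lower pair. Either add an absolute lower limit, set by the sponsor, or say why none is used.
3. Update Table 14.3.2.2 and Listing 16.2.13.2 to match.

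The cost is a few lines of SAP text and a few table rows, on data already collected at every visit. The downside is some chance flags, mostly at the 20 bpm step. Reporting the 20 and 30 bpm steps in separate rows lets a reader discount the noisier one.
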